9. DESIGN

We will use a Hybrid I implementation randomized-controlled design to simultaneously gather outcomes regarding the intervention's feasibility and process data to facilitate wide-spread implementation and dissemination of the intervention into clinical practice if the intervention is effective. A total of 80 patients will be recruited on a rolling basis. Forty will be randomized to intervention and 40 to control.

10. TREATMENT

The planned evidence-based behavioral intervention using techniques associated with effective dietary change in older adults (Table 1): problem solving, plan social support, goal setting, follow-up prompts, and provide feedback. The 6-month intervention will likely consist of the following, although aspects of the intervention may change based on data from the adaptation process: 1) Mailed educational materials about the importance of consuming cruciferae, how to maximize urinary ITC levels, serving size goals, the importance of self-monitoring, and strategies to increase intake, along with booklets to record daily cruciferae intake; 2) One live phone call (~45-60 minutes) delivered two weeks after mailing materials to verify understanding of the educational information and help participants complete a personalized action plan where participants will identify barriers and facilitators (e.g. social support) to meet identified goals (problem solving); 3) 11 Interactive Voice Response (IVR) phone messages that will begin by asking participants to input the servings of cruciferae consumed the previous week (follow-up prompt). Depending on number of servings participants input, they will be routed to one of three paths: a) meeting goals, b) not meeting goals but has some progress, c) no progress. Participants on each path will receive a tailored phone message (provision of feedback) selected from a library of messages to enable participants to meet or maintain their cruciferae goal. A total of 11 IVR calls will be delivered weekly for the first three weeks and then bi-weekly for the remainder of the 6-month intervention.

Table 1. Intervention Components

Intervention component	Intervention content/ behavior technique	SCT Construct	CAB adaptation
Educational Materials	
 Relationships between cruciferae, ITC yield, and bladder cancer Type of vegetable, cooking methods, and timing of intake for maximum ITC exposure Program goal of 1 serving of cruciferae per day/Goal setting Keeping track of servings eaten per day 	
 Knowledge Outcome expectations Behavioral skills Barriers and opportunities Intentions 	
 Barriers and facilitators to meeting goals, examples from BCS day-to-day life, strategies to meet goals, visuals pleasing to BCS
1 Live phone call	
 Review materials Action plan to meet program goal/problem solving 	
 Knowledge Behavioral skills Barriers and opportunities Self-efficacy 	
 Potential problems and subsequent solutions for BCS to meet goals
11 Interactive Voice Response (IVR) phone calls	
 Participants enter by phone servings of cruciferae eaten in prior week/follow-up prompt Automated feedback based on the extent participants met program goal/ feedback 	
 Barriers and opportunities Reinforcement Self-efficacy 	
 How to structure the cruciferae intake form to make it easy for BCS to use Construct library of IVR feedback messages relevant to BCS

11. PROCEDURES INVOLVED

Aim 1: Develop an evidence-based behavioral intervention to increase cruciferous vegetable intake

Adaptation. Working with our Community Advisor Board (CAB) consisting of a urologist, clinic staff, and BCS, we will refine current evidence-based vegetable interventions to develop a novel dietary intervention for BCS. We will use a systematic process consisting of information gathering, discussion groups, and mock intervention delivery. [name], who has extensive experience adapting evidence-based behavioral interventions for diverse groups, will lead the team through a four-stage adaptation process based on the Barrera and Castro framework⁴² and PEN-3 model for cultural adaptation⁴³. We will: 1) identify relevant factors to increase cruciferae intake in BCS; 2)

use the PEN-3 model to review each of the intervention's components (e.g. graphics, terminology, saliency of behavioral messages); 3) administer the revised intervention to the CAB for their feedback; and 4) refine the intervention based on Step 3. We will also present the program to the BCS group meeting at Roswell Park to ensure the intervention is salient to our target population by demographic characteristics. The final product will be a 6-month cruciferae intervention for BCS grounded in Social Cognitive Theory (SCT). CAB members will each be compensated \$100 per meeting (up to three meetings), each meeting lasting about 1.5 hours and will be conducted via phone or computer. CAB members (bladder cancer survivors) may be asked to complete a structured interview over the phone and complete some demographic questions about themselves. Structured interviews will last approximately 60 minutes and CAB members will be paid \$50 for completion of the structured interview. See Appendix K for Study Information Sheet for CAB members and Appendix L for CAB Interview Guide)

Intervention Design. Drawing from the large body of literature on evidence-based behavioral fruit and vegetable interventions, the intervention will likely include components used by Wolf et al.⁴⁴ and Djuric et al.⁴⁵ (i.e. educational materials, phone calls, written plans, self-monitoring), who significantly increased vegetable intake among participants whose demographic characteristics mirror the majority of our target population (i.e. age 65 and older, diverse, male). The following evidence-based behavioral techniques associated with effective dietary change in older adults⁴⁶ will also be incorporated (Table 1): *problem solving, plan social support, goal setting, follow-up prompts, and provide feedback*. The 6-month intervention will likely consist of the following, although aspects of the intervention may change based on data from the adaptation process: 1) Mailed educational materials about the importance of consuming cruciferae, how to maximize urinary ITC levels, serving size goals, the importance of self-monitoring, and strategies to increase intake, along with booklets to record daily cruciferae intake (See Appendix P); 2) One live phone call (~45-60 minutes) delivered two weeks after mailing materials to verify understanding of the educational information and help participants complete a personalized action plan where participants will identify barriers and facilitators (e.g. *social support*) to meet identified goals (*problem solving*) (See Appendix Q); 3) 11 Interactive Voice Response (IVR) phone messages that will begin by asking participants to input the servings of cruciferae consumed the previous week (*follow-up prompt*). Depending on number of servings participants input, they will be routed to one of three paths: a) meeting goals, b) not meeting goals but has some progress, c) no progress. Participants on each path will receive a tailored phone message (*provision of feedback*) selected from a library of messages to enable participants to meet or maintain their cruciferae goal. A total of 11 IVR calls will be delivered weekly for the first three weeks and then bi-weekly for the remainder of the 6-month intervention. The CAB will give specific feedback about visual material that would be the most appealing to BCS, specific barriers survivors may have to meet study goals, examples from survivors' day-to-day lives to incorporate in the materials, specific phrases and language to clearly convey the content, strategies to consume cruciferae with minimum effort, and tailored wording or terms that would optimize the participants' response to IVR feedback. We selected phone and mail modalities of intervention delivery because: 1) Phone-based dietary interventions are effective³⁵; 2) phone-based interventions are more feasible to implement on a wide-scale compared to face-to-face interventions, which take more resources⁴⁷; 3) IVR would be more cost-effective for a clinic to incorporate within its system vs. dedicating staff to provide frequent calls. Further, IVR is more feasible and accessible to the target population because BCS are typically older (average age at diagnosis is 73 years old); use of text messaging is lower among older groups, with less than half reporting email or text messaging for communication⁴⁸.

Control intervention. Participants in the control arm will receive mailed materials about general fruit and vegetable intake intervention based on published NCI guidelines. (<https://cancercontrol.cancer.gov/ocs/>). The control intervention will utilize the same delivery method (i.e. mailed educational materials, live phone call, IVR calls) and follow the same contact schedule as the treatment schedule (See Appendix P and Appendix Q). We intend to compare our tailored cruciferae program with general program on increase of fruit and vegetable intake. We anticipate minimal contamination between intervention and control because BCS will be recruited throughout our catchment area and our intervention will be delivered individually with each BCS.

Personnel Training. [name] will utilize her extensive experience in training others in the delivery of behavioral interventions to train project staff to implement the intervention. A training-of-trainers model that incorporates didactic education, trainee practice, and written and verbal feedback will be used. Training will build knowledge about behavior change promotion, with a specific emphasis on delivering the live phone call with fidelity, utilizing participant booklets to program the IVR messages, and communicating effectively with participants about health. The training will conclude with project staff demonstrating mastery of concepts through mock phone sessions and live phone calls, and accurate programming based on booklet data received. Project staff will be asked to complete a checklist of topics to monitor intervention fidelity.

Aim 2: Conduct a feasibility pilot of our evidence-based dietary behavioral intervention

Study Design. We will use a Hybrid I implementation randomized-controlled design to simultaneously gather outcomes regarding the intervention's feasibility and process data to facilitate wide-spread implementation and dissemination of the intervention into clinical practice if the intervention is effective. A total of 80 patients will be recruited on a rolling basis. Forty will be randomized to intervention and 40 to control.

Participant Recruitment. Eligibility criteria include: 1) English speaking; 2) diagnosed with stage Tis, Ta, or T1 bladder cancer; 3) resides in the Western New York (WNY) catchment area (Niagara, Orleans, Genesee, Erie, Wyoming, Chautauqua, Cattaraugus, and Allegany counties); 4) did not receive a partial or radical cystectomy; 5) does not have a prior cancer diagnosis within 12 months of their bladder cancer diagnosis 6) does not have a subsequent more advanced bladder cancer diagnosis; and 7) (for Roswell Park Cancer Registry only) diagnosed 2016-2018, 2019-current. We chose not to include current cruciferae intake as an eligible criterion because prior studies have reported that BCS consumed an average of 0.44-0.45 servings per day^{12, 26}, less than half our recommended amount. Using ICD-O-3 codes provided, [name] of the NYSCR will lead her staff to identify qualifying patients from their database based on the study's eligibility requirements. The NYSCR has identified 199 cases that meet the study's eligibility criteria in 2018 and anticipate at least 400 eligible cases in total in 2018 and 2019. A total of 250 eligible patients will be contacted to enable researchers to recruit from a pool of at least 100 patients. In prior studies, 52.4% to 62.5% of patients contacted by the NYSCR agreed to be contacted by researchers for study consent. The NYSCR will send a letter to the physician of record for selected cases notifying that the patient was identified for the study, requesting that the NYSCR be notified if the patient is unable or ineligible to participate in the study, and requesting information about the case's primary care physician if different from the contacted physician. If no contraindication has been received from the physician or if the physician has not responded within 3 weeks, the NYSCR will send an informational packet to the patient. The packet will contain: 1) a letter with study information; 2) a participant information sheet; and 3) a release of information consent form. After two weeks without response, a reminder packet will be sent and followed with up to five phone

calls. If the NYSCR can't reach the patient, the patient will be considered a refusal. The NYSCR's materials and procedures will be reviewed by the New York State Department of Health IRB. For patients who agree to be contacted about the study, the NYSCR will securely share the patient's name, contact information, and information about their diagnosis with the Roswell study team. For the Roswell Park Cancer Registry, study staff will consult with Roswell Park urologist to determine if the patient is unable or ineligible to participate in the study. The patients accessioned from the Roswell Park Cancer Registry will be contacted by letter (See Appendix T) asking them to participate in the study. Study staff will follow-up with potential participants to determine whether they received the letter and if they are interested in participating. We estimate that from the pool of at least 100 patients who consent to be contacted, we will be able to obtain informed consent from at least 80 patients (80%). The Roswell study team will share information with the NYSCR team on the patients who agree to participate in the study, as well as any information obtained from study participants that does not match the information provided from the NYSCR database (e.g., race, ethnicity).

Participant Data and Sample Collection Procedures. Research staff will contact patients who have agreed to be contacted by phone, whereby they will provide a general study overview and conduct a screening interview to confirm eligibility. The consent form will be mailed out to patients prior to the consenting discussion. We will ask the patient to mail back the consent form with the appropriate signatures. We will also provide an additional copy of the consent form for their records. We will include a paid postage pre-addressed envelope for the patient to mail back the signed consent form to study staff. Baseline Data Collection will be conducted within four weeks prior to intervention start. The Data Collector, masked to treatment assignment, will conduct telephone surveys with participants and directly enter participants' responses into pre-programmed data collection forms in REDCap^{49, 50}. Surveys will cover sociodemographic variables, faith and spirituality beliefs, dietary, and cruciferae intake (Appendix F). Additionally, 24-hour dietary recalls will be conducted and instructions (Appendix M) and a reference guide (Appendix N) will be mailed out to participants prior to their scheduled recall interview. Participants will also be mailed out track books to help keep track of their fruit and/or vegetable intake during the intervention (Appendix R). Follow-up Assessment (Appendix G1) will be conducted at 6 months following the same protocol as the baseline assessment (Appendix F). Participants will receive \$100 for completing the baseline and 6-month follow-up assessments. In addition, we will ask participants' feedback on the intervention (Appendix G2) as part of the Follow-Up Assessment (Appendix G1). The feedback questions (Appendix G2) will be given to those in the cruciferous arm only. For cruciferous arm study participants that have completed the 6-month follow-up assessment as of the March 21, 2022 Protocol revision, the study participants will be called back to complete the feedback questions (Appendix G2). These study participants will first be sent an information sheet (Appendix W) regarding the additional feedback questions before being called. When they are called regarding the study feedback questions, they will provide verbal consent before proceeding with answering the feedback questions.

Urine Sample Collection will be conducted at baseline and 6-months. Participants will be instructed to collect first-void urine continuously for three days, which will provide a more reliable measurement than one-spot urine samples. A specially designed urine collection device consisting of a 10-mL container and sponge with a plastic holder will be used, which does not impact urinary ITC measurement and has been used in the Be-Well study with documented ease of collection and minimal shipment burden. Staff will mail urine collection kits and instructions (Appendix C) to participants. Given that recent behaviors may have a large impact on urinary ITC levels,

participants will be asked to complete a brief 2-page specimen collection survey (Appendix D) on medical and lifestyle status in the past two days. They will then return the survey and urine samples to Roswell Park in the provided shipping box with biohazard labels and ice packs via pre-paid overnight shipping service. Once received, the urine will be spun down from the sponge, aliquoted, and stored at -80°C at [name] lab ([name]) at Roswell Park. The urine aliquots will be assayed at [name] for ITC analysis using HPLC-based cyclocondensation assay⁶⁴ This method is able to accurately measure as low as a few picomoles of ITCs and their metabolites. [name] lab has experience and expertise in running this assay⁶⁵ and will process the urine samples and perform the measurements. The results will be adjusted by urinary creatinine level, which will also be performed in the laboratory, using a commercially available creatinine assay kit (Caymen, Ann Arbor, MI). The cell pellets from three urine samples per participant will be combined and delivered to Genomics Shared Resources at Roswell Park for RNA-seq analysis in a batch. Additional urinary metabolites and potential biomarkers will be explored using proteomic and/or metabolomic approaches. All assays will be conducted on the stored urine samples. Neither new urine sample collection nor patient contact will occur.

Exploratory Aim: Engage providers to ascertain specific clinic-level implementation factors

We will ask intervention participants to nominate physicians to participate in a short 15-minute semi-structured interview. Research staff will mail an invitation letter to nominated physicians that will include an information sheet (Appendix J), opt-in/opt-card card, and stamped reply envelope. Within 2-weeks, physicians who do not respond will be contacted by phone, fax, or email with no more than 5 attempts. Participating physicians will receive \$100. Physicians who verbally consent to participate will be asked to refer other physicians to the study. CAB members will also utilize their networks to nominate physicians for staff to contact.

We will conduct brief 15-minute semi-structured interviews using an interview guide. The guide will give physicians a brief overview of our cruciferae intervention. Research staff will then ask questions regarding facilitators and barriers of intervention adoption within clinical practice³⁷. Staff will ask physicians the needed implementation strategies to sustain the intervention post research funding, in addition to intervention modifications to maximize sustained clinic adoption³⁷.

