3. INCLUSION AND EXCLUSION CRITERIA

Inclusion Criteria

Cancer Patient:

To be included in this study, participants must meet the following criteria:

1. Age 18 years old or older (no upper limit).
2. English speaking.
3. Diagnosed with stage Tis, Ta, or T1 bladder cancer.
4. Resides in the Western New York catchment area.
5. Did not receive a partial or radical cystectomy.
6. Does not have a prior cancer diagnosis within 12 months of their bladder cancer diagnosis.
7. Does not have a subsequent more advanced bladder cancer diagnosis.
8. For Roswell Park Cancer Registry only: Bladder cancer diagnosed 2016-2018, 2019-current.
9. Participant must understand the investigational nature of this study and sign an Independent Ethics Committee/Institutional Review Board approved written informed consent form prior to receiving any study related procedure.

Physician:

To be included in this study, physicians must meet the following criteria:

1. English speaking.
2. Physician in a clinic located in the catchment area.
3. Currently treats bladder cancer patients.

Refer to **Appendix A** for the Investigator Study Eligibility Verification Form: Inclusion Criteria.

Exclusion Criteria

Cancer Patient:

Participants Recruitment will be excluded from this study for the following:

1. Participants who have had chemotherapy or radiotherapy within 4 weeks (6 weeks for nitrosoureas or mitomycin C) prior to entering the study or those who have not recovered from adverse events due to agents administered more than 4 weeks earlier.
2. Participants with known brain metastases should be excluded from this clinical trial because of their poor prognosis and because they often develop progressive neurologic dysfunction that would confound the evaluation of neurologic and other adverse events.
3. Adults unable to consent.
4. Adults unable to complete study measures in English.
5. Individuals who are not yet adults (infants, children, teenagers).
6. Uncontrolled intercurrent illness including, but not limited to, ongoing or active infection, symptomatic congestive heart failure, unstable angina pectoris, cardiac arrhythmia, or psychiatric illness/social situations that would limit compliance with study requirements.
7. Unwilling or unable to follow protocol requirements.

Physician:

1. Unable to complete the study measures in English.

Refer to **Appendix B** for the Investigator Study Eligibility Verification Form: Exclusion Criteria.

Inclusion of Women and Minorities

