
Roswell Park Cancer Registry. Due to low enrollment from the NYS Cancer Registry, we will also recruit participants from the Roswell Park Cancer Registry that meet the study's eligibility criteria. To avoid overlap with NYS Cancer Registry patients, we will identify potential participants by focusing on patients diagnosed within last five years and exclude patients diagnosed within 2018-2019 (original parameters for the NYS Cancer Registry recruitment list). Study staff will consult with Roswell Park urologist to determine if the patient is unable or ineligible to participate in the study. The patients accessioned from the Roswell Park Cancer Registry will be contacted by letter (See Appendix T) asking them to participate in the study. Study staff will follow-up with potential participants to determine whether they received the letter and if they are interested in participating.

Physician Recruitment. We will ask intervention participants to nominate physicians to participate in a short 15-minute semi-structured interview. Research staff will mail an invitation letter to nominated physicians that will include an information sheet (Appendix J), opt-in/opt-card card, and stamped reply envelope. Within 2-weeks, physicians who do not respond will be contacted by phone, fax, or email with no more than 5 attempts. Participating physicians will

receive \$100. Physicians who verbally consent to participate will be asked to refer other physicians to the study. Community Advisory Board (CAB) members will also utilize their networks to nominate physicians for staff to contact. We will recruit up to 20 physicians to ensure data saturation⁶¹. Among clinicians involved in cancer treatment, enrollment rates between 46.3%-92% have been reported^{60, 62, 63}, with one study reporting an enrollment rate of 48% among clinicians involved in bladder cancer treatment⁶². Out of the 80 participants enrolled in our intervention, we anticipate 40 to nominate their physicians and we expect to receive referrals for 5 additional physicians from enrolled physicians and 5 physicians nominated by our CAB. Given an anticipated enrollment rate of 48%, we anticipate recruitment of 20 physicians.

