Appendix L Bladder Community Advisory Board (CAB) Interview Guide

Thank you for being willing to be a part of helping us make a healthy eating program for bladder cancer survivors to improve their health. We're going to start by asking some questions about you.

1. (Administer demographic survey, page 2)
2. When were you first diagnosed with bladder cancer?
 - What type of treatment did you receive after your bladder cancer diagnosis?
 - How long did the treatment last?
3. Have you had any recurrence since your initial bladder cancer diagnosis?
 - If yes, when did it happen and what treatment did you receive?
4. What is the biggest concern you have regarding your bladder cancer diagnosis?
5. Since your bladder cancer diagnosis, did you change your eating habits?
 - If yes, how did you change your eating habits?
6. Do you think what you eat can make a difference in terms of bladder cancer prevention or recurrence?
 - If yes, how?
7. Recent research has shown that eating more cruciferous vegetables can reduce the chances of bladder cancer coming back in bladder cancer survivors. Cruciferous vegetables include broccoli, arugula, brussels sprouts, green or white cabbage, and turnips.
 - What do you think about this information? Is this helpful? Have you heard this before?
8. In your day-to-day life, what might make it easier for you to eat more cruciferous vegetables?
 - Probes: Help from your family, help from the healthcare system, help from friends, any particular information
9. Who does most of the shopping for food in your family?
 - If self: What affects the kinds or amount of vegetables you buy?
 - If not self: What role do you play in what they shop for?
10. Who does most of the planning or preparing of meals in your family?
 - If not self: What role do you play in how meals are planned or prepared?
11. How do other people in your life impact the kinds and amounts of vegetables you eat?

Demographic Survey

• **Are you male or female?**

- 1 Male
- 2 Female

• **Are you Hispanic or Latino/a or Spanish in origin?**

- 1 Yes

Are you:
(circle all that apply)

- 1 Mexican, Mexican American, Chicano/a
- 2 Puerto Rican
- 3 Cuban
- 4 Another Hispanic, Latino/a, or Spanish origin

- 2 No

• **Which one or more of the following would you say is your race? (Circle all that apply)**

- 1 White
- 2 Black or African American
- 3 American Indian or Alaska Native
- 4 Asian
- 5 Other (please specify)_____

• **How old are you?**

_____ years

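### Survivors exposed to the cruciferae programme during its development are neither excluded nor identified at screening, so they can be randomized to either arm

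*Combined protocol and SAP*

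**What the plan says.** Section 11, Aim 1, describes a Community Advisory Board "consisting of a urologist, clinic staff, and BCS", where BCS means bladder cancer survivors. In the third adaptation step the team will "administer the revised intervention to the CAB for their feedback". The same paragraph continues: "We will also present the program to the BCS group meeting at Roswell Park to ensure the intervention is salient". Survivors on the board may also be interviewed, and the guide in Appendix L tells them: "Recent research has shown that eating more cruciferous vegetables can reduce the chances of bladder cancer coming back in bladder cancer survivors".

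Section 5 says that, because enrolment through the state registry was low, "we will also recruit participants from the Roswell Park Cancer Registry". The only criterion specific to that source is the diagnosis period: "For Roswell Park Cancer Registry only: Bladder cancer diagnosed 2016-2018, 2019-current" (Section 3).

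On contamination, Section 11 (Control intervention) states: "We anticipate minimal contamination between intervention and control because BCS will be recruited throughout our catchment area". Its other reason is that the programme is delivered to each participant individually.

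Section 19 randomizes 1:1 in permuted blocks, with no stratification by recruitment source or prior exposure.

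**The concern.** Both arms use the same delivery method and contact schedule, so the trial contrasts content. The intervention teaches which vegetables to choose, light cooking, eating them at dinner time and a goal of one serving a day. A survivor who has been through the mock delivery, or has heard the programme presented, already holds some or all of that content.

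In the control arm, such a person may act on it and move towards the intervention arm. In the intervention arm, they may start from a raised baseline with less room to change. Either tends to shrink the primary contrast in urinary ITC and cruciferae intake. A pre-exposed control may also recognise which programme they were given, and intake is self-reported. Adjusting for baseline helps only in part: the planned R² is 0.2, and the baseline value cannot capture a control who takes up the earlier message after baseline.

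**Working it through.** **1. Can exposed people be enrolled?** Each place that could stop or flag them was checked.

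- Section 3, patient inclusion and exclusion criteria and special populations: nothing on advisory-board membership, mock delivery or the survivor-group presentation. The criteria repeated in Section 11 (Aim 2) add nothing.
- Appendices A and B, eligibility checklists: the same lists, equally silent.
- Appendix E, phone screen: asks about stage, cystectomy, other cancer, recent chemotherapy or radiotherapy, and health conditions. It has no question on earlier contact with the programme.
- Appendix H, state registry search: filters on stage, county, age, treatment, other cancers, death and research opt-out only.
- Section 5, urologist consultation for Roswell patients: checks inability or ineligibility, but the criteria applied do not mention exposure.

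**2. Does the contamination statement cover it?** Geographic spread and individual delivery limit contact between participants once enrolled. A board meeting or survivor-group presentation is a shared event outside the randomized delivery, so neither reason applies.

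**3. The plan's own power figure.** Inputs from Section 19: n = 40 per arm, difference 0.57 SD, R² = 0.2, two-sided α = 0.05, SD 8.9 µM for ITC.

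Noncentrality = (Δ/SD) / √(1 − R²) / √(2/n), with df = 80 − 3 = 77 and critical t = 1.991.

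At 0.57 SD: 0.57 / √0.8 / √0.05 = 2.85, giving power 0.804. The stated 80% reproduces. In units, 0.57 × 8.9 = 5.07, which the plan rounds to 5.1 µM. At 5.1 µM, Δ/SD = 0.573, the noncentrality is 2.865 and power is 0.808.

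**4. Dilution scenarios.** Let k of 40 controls be exposed and let exposure carry a fraction h of the effect. Diluted difference = 5.1 × (1 − h·k/40). Both k and h are assumptions, since the documents give neither.

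| k of 40 controls | h | Difference (µM) | Power |
|---|---|---|---|
| 0 | – | 5.10 | 0.81 |
| 2 | 1 | 4.85 | 0.77 |
| 3 | 1 | 4.72 | 0.74 |
| 2 | 0.5 | 4.97 | 0.79 |
| 3 | 0.5 | 4.91 | 0.78 |

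Only exposed controls are counted; any loss from exposed intervention participants with less room to improve is not added.

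**5. At the stated goal.** The 5.1 µM is what the design can detect, not what it aims for. The ITC goal is 4.4 to 10 µM, a rise of 5.6 µM. If controls do not change (an assumption), power at 5.6 µM is 0.87. With 2 or 3 fully exposed controls the difference is 5.32 or 5.18 µM and power is 0.84 or 0.82.

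**The case against.** The strongest reply is that the effect is small and the exposure weak. The documents describe one advisory board and one group meeting. Board contact is at most three meetings of about 1.5 hours plus a possible interview; the programme itself is mailed materials, a long live call, weekly track books and 11 automated calls over six months. Equating the two overstates dilution. At half effect the loss is 2 to 3 percentage points of power, and at the stated 5.6 µM goal the trial stays above 80% in the scenarios shown. This is a pilot with low enrolment, and some participants may have finished follow-up by the March 2022 revision. All of that stands. It limits the size of the problem but does not close the gap.

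Three stronger readings are tempting and are not supported:

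- A reader might carry the scenarios up to 4 or 8 exposed controls of 40, where full-effect power is about 0.72 or 0.62. Under 1:1 allocation that means about 8 or 16 exposed people among 80, and nothing in the documents suggests so many.
- A reader might infer that exposed participants could never be traced. Board members are paid per meeting and may complete an interview and demographic survey, so the team presumably knows who they are. Only attendance at the survivor-group presentation is not described as recorded.
- A reader might infer that the Roswell registry creates the problem. Patients found through the state registry could also attend the Roswell group, and no text says that attendees belong to the Roswell registry or meet its diagnosis years.

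The text of Appendix K, the advisory-board information sheet, was not available, so it is unknown whether board members were told they could not enrol.

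**Conclusion.** The gap is real and modest. As the visible text stands, survivors given the cruciferae content during development can pass every eligibility step and be allocated to either arm, and the contamination argument does not address them. The Roswell source probably raises the likelihood.

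The size cannot be established from the documents. The range of 0.74 to 0.79, against about 0.81 without exposure, assumes 2 to 3 exposed controls, half to full effect, and a true difference equal to the 5.1 µM detectable difference. It is illustrative and not an estimate. No stated figure is in error: the 80% power reproduces. The point deserves action because the bias runs towards no difference and prevention is cheap.

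**What to change.** 1. Add an exclusion to Section 3 and Appendix B covering anyone who served as a survivor member of the advisory board, received the mock intervention, or attended the survivor-group presentation.
2. Add one question to the Appendix E phone screen, worded neutrally so that it does not reveal the cruciferae content. It could ask whether the person has taken part in any meeting, interview or trial run connected with developing this programme.
3. Check names against the advisory-board roster before randomization.
4. For anyone already randomized, record exposure (none, presentation, or board/mock delivery). Keep them in the primary ANCOVA and report a sensitivity analysis without them. With two or three such people this will show little beyond whether the result depends on them.
5. If Appendix K already bars board members from enrolling, repeat the rule in the eligibility section so that screening staff apply it.

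The cost is one criterion, one question and a few eligible patients in a trial that is already short of them. If the places are refilled to 40 per arm with unexposed patients, power returns to the stated 80%. If exposure proves to be nil, a sentence recording that is enough.
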